5 STUDY DRUG

5.1 Study Drug Supply, Route of Administration, and Storage

The study drug in this study is serlopitant 5 mg or placebo in a film-coated tablet formulation for oral administration. The serlopitant tablets contain microcrystalline cellulose, mannitol, croscarmellose sodium, silicon dioxide, sodium lauryl sulfate, and magnesium stearate, and are film coated with Opadry® Brown. The placebo tablets contain microcrystalline cellulose, lactose monohydrate, and magnesium stearate, and are film coated with Opadry® Brown.

The study drug will be provided in bottles that can be stored at room temperature (59-86°F, 15-30°C).

The tablets will be supplied in bottles, with 18 tablets per bottle. One bottle will be issued via Interactive Web Response System (IWRS) at baseline and at Weeks 2 and 4, and two bottles will be issued via IWRS at Week 6. A total of 5 bottles will be dispensed to subjects completing 10 weeks of study drug treatment.

Additional details regarding study drug supplies can be found in the Pharmacy Manual.

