5.3 Dosing Regimen

Subjects will take a loading dose (3 tablets taken orally) at the site on the first day of the treatment period (Study Day 1). Starting on Study Day 2, subjects will take one tablet per day taken orally. Subjects will be instructed to take all doses from Study Day 2 onward once a day. Study drug may be taken with or without food.

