5.9 Treatment Compliance

Records of study drug used, dosages administered, and intervals between visits will be kept during the study. Subjects will record in the eDiary the doses administered, as well as whether a dose was taken within 2 hours of eating a meal. Subjects will be asked to return all partially used and empty bottles to the study site at each visit. The site staff will count and record the number of remaining tablets in each returned bottle. The site staff will review the subject's eDiary to help evaluate compliance with dosing at each study visit. Discrepancies between compliance as assessed by tablet counts and doses recorded in the eDiary will be reconciled and documented. Dosing dates and times will be recorded. A subject who has deviated significantly from the once-daily dosing regimen will be counseled.

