The Baseline visit occurs between 14 to 31 days after the screening visit, depending on the required washout period following discontinuation of excluded therapies. Eligibility must be confirmed prior to randomization. At the Baseline visit, the following procedures and assessments are to be performed, preferably in the order shown below:

- Ask the subject to complete the DLQI, HADS, and ESS questionnaires
- Assess and record any changes in the subject's concomitant medications
- Assess and record any changes in the subject's medical history
 - Female subjects should be queried regarding history of, or current, breast masses or abnormal discharge, and history of mammography (if applicable), and history of abnormal vaginal bleeding or discharge
- Review menstrual diary and record dates of menstrual flow (if applicable)
- Assess AE's and record SAEs caused by protocol-mandated interventions
- Obtain vital signs
- Perform a urine pregnancy test for females of childbearing potential and confirm the subject has a negative urine pregnancy test result prior to randomization (with positive or equivocal results confirmed by a serum pregnancy test)
- Confirm subject's eligibility based on the inclusion/exclusion criteria (to include review of eDiary compliance for eligibility)
- Randomize subject in IWRS if eligibility confirmed
- Perform targeted physical examination, including weight
- Perform IGA PN-A

- Perform IGA PN-S
- Obtain photos (at selected sites, only subjects that signed photography consent)
- Dispense study drug; subjects will take loading dose of 3 tablets while on site
- Review eDiary for compliance, re-train subject as needed
- Assess and record any post-dose AEs and SAEs
- Confirm next scheduled visit

6.5.5 *Week 1 Telephone Contact Visit*

The Week 1 visit is a telephone visit that occurs 7 days (\pm 3 days) after the Baseline visit. At the Week 1 visit, the following procedures and assessments are to be performed:

- Assess and record any changes in the subject's concomitant medications
- Assess and record any AEs and SAEs
- Review eDiary for compliance, re-train subject as needed
- Confirm next scheduled visit

6.5.6 *Week 2 Visit*

The Week 2 visit occurs 14 days (\pm 3 days) after the Baseline visit. At the Week 2 visit, the following procedures and assessments are to be performed:

- Assess and record any changes in the subject's concomitant medications

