- Perform targeted physical examination, including weight
- Assess and record any AEs and SAEs
- Collect returned study drug
- Utilize IWRS to assign new bottle of study drug
- Review eDiary for compliance, re-train subject as needed
- Confirm next scheduled visit

6.5.9 *Week 10 Visit*

The Week 10 visit occurs 70 days (\pm 7 days) after the Baseline visit. At the Week 10 visit, the following procedures and assessments are to be performed:

- Ask the subject to complete the DLQI, HADS, and ESS questionnaires
- Assess and record any changes in the subject's concomitant medications
- Female subjects should be queried for presence of new breast masses or abnormal discharge, and abnormal vaginal bleeding or discharge
- Review menstrual diary and record dates of menstrual flow (if applicable)

- Obtain ECG
- Obtain vital signs
- Perform targeted physical examination, including weight
- Perform IGA PN-A
- Perform IGA PN-S
- Perform a urine pregnancy test for females of childbearing potential (with positive or equivocal results confirmed by a serum pregnancy test)
- Draw blood for clinical laboratory tests (morning blood sampling due to Endocrine assessments)
 - Reproductive endocrine labs for females under 55 years of age at consent
 - Endocrine
 - Hematology
 - Chemistry
- Collect PK blood sample
- Assess and record any AEs and SAEs
- Collect returned study drug
- Obtain photos (at selected sites, only subjects that signed photography consent)
- Review eDiary for compliance, inform subject to continue entering WI-NRS score until Follow-up visit
- Review study drug compliance with re-training as required
- Confirm next scheduled visit date

6.5.10 ***Post-Drug Observation Visits***

There are five (5) post-drug observation visits, and a Follow-up visit to complete the post-observation period.

The Post-Drug Observation Visits occur 3 days (± 1 days), 7 days (± 3 days), 14 days (± 3 days), 21 days (± 3 days), and 28 days (± 3 days) after the Week 10 Visit.

At the Post-Drug Observation Visits, the following procedures and assessments are to be performed:

- Ask the subject to complete the HADS and ESS questionnaires
- Assess and record any changes in the subject's concomitant medications
- Female subjects should be queried for presence of new breast masses or abnormal discharge, and abnormal vaginal bleeding or discharge
- Review menstrual diary and record dates of menstrual flow (if applicable)
- Obtain vital signs
- Assess and record any AEs and SAEs

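### The 18-tablet Baseline bottle lasts only through Day 16, but the Week 2 visit may fall as late as Day 18: a minor supply/window mismatch

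*Protocol*

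**What the plan says.** Protocol 5.1 states the bottle size, "The tablets will be supplied in bottles, with 18 tablets per bottle", and the schedule: "One bottle will be issued via Interactive Web Response System (IWRS) at baseline and at Weeks 2 and 4, and two bottles" at Week 6. It also gives the total: "A total of 5 bottles will be dispensed to subjects completing 10 weeks of study drug treatment". Further supply details are left to the Pharmacy Manual, which is not among the documents.

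Under Protocol 5.3, three tablets are taken at the site on Day 1. After that, "Starting on Study Day 2, subjects will take one tablet per day taken orally". Section 5.5 has any dose not taken documented as missed.

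On timing, Protocol 6.5.6 says "The Week 2 visit occurs 14 days" after Baseline, with a tolerance of 3 days either way. Appendix A, Table 2 counts visits from Baseline as Day 1. The Week 2 visit includes a PK sample and the next bottle.

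On leftovers, Protocol 5.9 says: "Subjects will be asked to return all partially used and empty bottles to the study site at each visit". No section says whether returned tablets may be handed back.

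For Week 6, Section 5.1 says "two bottles will be issued via IWRS at Week 6", while the visit list in 6.5.8 says "Utilize IWRS to assign new bottle of study drug", the line also used at Weeks 2 and 4.

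**The concern.** The dispensing schedule, the visit window and the daily dosing instruction cannot all be met at the late end of the Week 2 window. A subject who attends on a permitted day can have no tablet for a day on which one is due. The record then shows a missed dose that the plan itself caused.

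The gap falls just before a PK draw. SAP 6.10 and Table 14.3.1.9 summarise concentrations by visit without regard to time since the last dose, so an affected sample enters the Week 2 summary as if it reflected once-daily dosing.

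**Working it through.** **Inputs.** 18 tablets per bottle; 1, 1, 1 and 2 bottles at Baseline, Weeks 2, 4 and 6 (Protocol 5.1). Three tablets on Day 1, then one a day (5.3). Visits at 14, 28 and 42 days (± 3) and 70 days (± 7) after Baseline (6.5). Half-life 45 to 86 h (1.5.1).

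**The plan's own total.** 1 + 1 + 1 + 2 = 5 bottles, or 5 × 18 = 90 tablets. This reproduces.

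**Day numbering.** With Baseline as Day 1, nominal Week 2 is Day 15 and its window is Days 12 to 18. The SAP 6.1.3 early-discontinuation example agrees: its Week 4 range runs from Day 22 to before Day 36, and (15 + 29)/2 = 22, (29 + 43)/2 = 36.

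**First interval.** Tablets needed through Day d are 3 + (d − 1). One bottle lasts to Day 1 + (18 − 3) = Day 16.

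| Week 2 visit | Needed through day before | Short | Needed including visit day | Short |
|---|---|---|---|---|
| Day 15 (nominal) | 16 | 0 | 17 | 0 |
| Day 16 | 17 | 0 | 18 | 0 |
| Day 17 | 18 | 0 | 19 | 1 |
| Day 18 | 19 | 1 | 20 | 2 |

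If Week 2 were instead read as Day 14, the latest visit would be Day 17, short by 1 only when that day's dose is due before the visit.

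**Later intervals, if returned tablets are not re-supplied** (visit-day dose taken from the new bottle):

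- Week 2 on Day 12 to Week 4 on Day 32: 20 doses, 18 tablets; Days 30 and 31 uncovered.
- Week 4 on Day 26 to Week 6 on Day 46: 20 doses, 18 tablets; Days 44 and 45 uncovered.
- Week 6 on Day 40 to Week 10 on Day 78: 38 doses, 36 tablets; Days 76 and 77 uncovered.

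Two adjacent intervals cannot both fall short, because the visit between them would have to be late for one and early for the other. One subject can therefore meet at most two of the four shortfalls.

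**If unfinished bottles carry forward.** Cumulative supply against need through the latest visit day is 36 against 34 (Week 4), 54 against 48 (Week 6) and 90 against 80 (Week 10). Only the first interval stays short, 18 against 20.

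**PK.** For a Day 18 visit the last possible earlier dose is on Day 16, about 48 h before the sample instead of 24 h. With simple exponential decline, the extra 24 h multiplies the concentration by 0.5^(24/45) = 0.69 or 0.5^(24/86) = 0.82: 31% to 18% lower.

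**Endpoint windows.** SAP 6.1.3 averages Days 8–14, 22–28 and 64–70 for Weeks 2, 4 and 10. The uncovered days (17–18, 30–31, 44–45, 76–77) lie outside all three, and outside Weeks 6 (36–42) and 8 (50–56).

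**Compliance.** Two shortfalls of 2 make 4 missed doses. With Week 10 on Day 78, 76/80 = 95%. With Week 10 on its earliest day, Day 64, SAP 6.9.1 expects 64 − 1 + 2 = 65 doses, and 61/65 = 94%. Both are well inside 80% to 120%.

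**The case against.** The case against acting is that this is a corner case. The nominal visit is covered, and a dose is certain to be lost only on the last permitted day. On Day 18 the visit-day tablet can come from the new bottle, which leaves one lost dose. The 90 tablets supplied exceed the 80 needed even through Day 78. Protocol 6.3 records dose and sampling times, so the population PK analysis can allow for the longer gap. The Pharmacy Manual may permit re-supply, and 6.5 allows unscheduled visits. All of this stands, and it limits the size of the point. It does not remove the contradiction, because Section 5.1 itself fixes one bottle at Baseline and no leftover exists to fill the first gap.

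Three stronger readings are tempting, and the documents do not support them.

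- **That staying in window forces 1 to 2 missed doses in every interval.** Week 2 visits on Days 12 to 16 lose none. The later gaps need opposite extremes at consecutive visits and no re-supply, and cannot occur in all four intervals for one subject.
- **That only one bottle is issued at Week 6.** A bottle started on Day 43 would end on Day 60 and leave Days 61 to 70, 10 of the last 28 days, without drug, including the primary averaging window. But the 6.5.8 line repeats the Week 2 and Week 4 wording and gives no count, whereas 5.1 gives two at Week 6 and five in total. The 10-day figure is hypothetical.
- **That the primary result or the Per Protocol set is compromised.** The windows and compliance figures above show otherwise.

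**Conclusion.** The mismatch is real and minor. As written, one bottle covers through Day 16 and the Week 2 window runs to Day 18. One dose is unsupplied for a Day 18 visit, two if that day's dose is due before the visit, and one for a Day 17 visit on that same condition. The later shortfalls, up to 2 tablets in at most two of the four intervals, depend on returned tablets not being re-supplied, which the documents leave open.

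The consequences are missed doses logged against in-window subjects and an affected Week 2 concentration about 18% to 31% lower. How many subjects would attend on Day 18 is not known. If, as an assumption, 5% to 10% did, the Week 2 mean would fall by roughly 0.05 × 18% = 0.9% to 0.10 × 31% = 3.1%. This rests on Baseline being Day 1, the Day 1 tablets coming from the Baseline bottle, and simple exponential decline. The Week 6 wording is an editorial matter.

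**What to change.** Reconcile Protocol 5.1, 5.9 and the visit windows on the supply side, so that tablets on hand last to the latest permitted next visit. This could be done through the IWRS dispensing quantity. Alternatively, state that unfinished bottles carry forward and add a spare bottle at Baseline; carry-forward alone would not close the first interval. The dosing regimen is not in question and need not change.

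As an editorial correction, make the Week 6 instruction in 6.5.8 agree with the two bottles in 5.1.

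The cost is an IWRS setting or one extra bottle per subject, a few words in the protocol, and slightly more drug supply and tablet counting.

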5.2 Labeling and Study Drug Accountability

The study drug will be appropriately packaged and labeled in bottles with 18 tablets per bottle. The study drug supplied for this study is not to be used for any purpose other than this study, and study drug accountability must be maintained for all bottles distributed to the investigative site.

Additional details regarding study drug labeling and accountability can be found in the Pharmacy Manual.

5.3 Dosing Regimen

Subjects will take a loading dose (3 tablets taken orally) at the site on the first day of the treatment period (Study Day 1). Starting on Study Day 2, subjects will take one tablet per day taken orally. Subjects will be instructed to take all doses from Study Day 2 onward once a day. Study drug may be taken with or without food.

5.4 Dose Modification

No dose modification of study drug will be allowed during this study.

5.5 Missed or Delayed Doses

Each dose of study drug after the first dose must be administered once daily. If a dose is missed, that dose will be considered and documented as a missed dose. Dosing should resume the next day.

5.6 Study Drug Discontinuation

Subjects should be discontinued from study drug treatment in the following situations:

- A female subject desires to become pregnant at the current time, stops contraception or expels her intrauterine device/implant, or becomes pregnant
- A female subject has new breast findings (e.g. a palpable mass or abnormal mammography, discharge), or has abnormal vaginal discharge or bleeding
- The subject decides to discontinue study drug treatment, or withdraws consent from the study
- The subject receives a strong CYP3A4 inhibitor (See [Appendix B](#))
- Any medical condition that may jeopardize the subject's safety if study drug is continued, in the investigator's and/or Sponsor's opinion; this may include the development of persistently (2 successive occasions) abnormal thyroid function tests (TSH >10, or TSH > 6 with low free T4; TSH <0.1, or TSH < 0.35 with high free T4); abnormal morning prolactin, cortisol, or corticotropin levels; or signs and symptoms of adrenal insufficiency

- Discontinuation is deemed to be in the best interest of the subject, in the investigator's and/or Sponsor's opinion, including evidence that the subject does not meet inclusion/exclusion criteria intended primarily for safety reasons, or a persistent lack of adherence to study procedures

The Sponsor or designee should be contacted within 24 hours of investigator's awareness of any study drug treatment discontinuation. Investigators should make every effort to contact the Sponsor or designee before discontinuing study drug treatment, if possible.

Subjects who discontinue treatment with study drug prior to completing the treatment period will enter a 5-week follow-up (post-study drug observation) period following the last dose of study drug (see [Section 3.1](#), [Section 6.5.10](#)). Every effort should be made for subjects to complete the 5-week observation period and the Follow-up visit after a subject has discontinued from study drug.

5.7 Prior, Concomitant, and Excluded Therapies

Prior therapies (including over-the-counter medications) used to treat the signs and symptoms of PN within the prior 2 years will be recorded for each subject at the Baseline visit.

Concomitant therapies include any therapies (including over-the-counter medications and bland emollients) used by a subject from initiation of study drug treatment through the follow-up period. A record of all medications used will be maintained for each subject throughout the study. Reported information will include a description of the type of drug, treatment period, dosing regimen, the route of administration, and drug indication. The use of any concomitant medication must relate to the subject's medical history or to an AE, except for vitamins/nutritional supplements, emollient use, and routine preventative immunizations.

5.7.1 *Allowed Therapies and Treatment Goals for Underlying Conditions*

Treatment of an underlying, treatable chronic pruritic condition is allowed, if stable for at least 6 weeks prior to the Baseline visit, and continued throughout the treatment period.

Treatment of the underlying systemic pruritic condition should be optimized per standard of care and treatment goals must be tailored based on age, sex, and concurrent health status and drug tolerance. While resolution of metabolic or endocrine disorders or eradication of an underlying infection may not always be feasible, every effort should be made to ensure the condition is well controlled, to prevent or reduce exacerbations and to prevent limitation on the activities of daily living. When applicable, laboratory evidence of control should be obtained. For example, if renal insufficiency is implicated as causal for pruritus, treatment would be expected to have meaningfully reduced the creatinine (compared to that at the time of diagnosis) and to maintain the creatinine at < 2.5 the ULN; control of diabetes is supported by a hemoglobin-A1c of < 7.5%; control of thyroid disease is supported by normalization of the thyroid stimulating hormone (TSH) or by a TSH within 1.5 times the ULN in elderly patients; iron deficiency is corrected with a serum iron within 0.8 times the lower limit of

normal; eradication of *Helicobacter pylori* infection generally requires a negative urea breath test and fecal antigen test and endoscopy; and the viral load should be undetectable if viral infections such as hepatitis B or hepatitis C, or HIV were previously diagnosed. Any previously active skin disease is considered to be well controlled if it is globally considered clear or almost clear (permissible to have post-inflammatory pigmentation, fine scale, faint pink erythema, barely perceptible induration/papulation, and no oozing or crusting).

Use of gentle cleansers and bland emollients (including those with urea) is encouraged for all subjects. If bland emollient use is elected, it must be initiated at least 2 weeks (14 days) prior to Baseline visit, and continued throughout the treatment period.

Treatment with non-systemic corticosteroids or antihistamines that do not involve skin application (e.g. inhaled, intranasal, ophthalmic, or intra-articular) is allowed.

Leukotriene inhibitors will be permitted for treatment of conditions other than PN (e.g. asthma).

5.7.2 *Excluded Therapies*

Initiation or use of topical therapy with corticosteroids, calcineurin inhibitors, calcipotriene, PDE-4 inhibitors is not permitted within 4 weeks prior to the Baseline visit or throughout the treatment period, but such therapy may be initiated during the follow-up period if needed.

Initiation of bland emollient is not permitted within 2 weeks (14 days) prior to Baseline visit or throughout the treatment period, but such therapy may be initiated during the follow-up period if needed.

The following therapies and activities are excluded from the Screening visit through the treatment period, and through the follow-up period:

- NK₁-R antagonists (other than study drug)
- Systemic immunosuppressive/ immunomodulatory therapies (including but not limited to systemic corticosteroids, PDE-4 inhibitors, cyclosporine, mycophenolate-mofetil, methotrexate, azathioprine, thalidomide, interferon-gamma, or phototherapy)
- Biologic therapies (other than therapies such as insulins, vaccines)
- Strong CYP3A4 inhibitors (See [Appendix B](#))
- Use of an indoor tanning facility, or natural sun exposure resulting in significant tanning or sunburn
- Any investigational therapy

The following therapies and activities are excluded from the Screening visit through the treatment period, and use is discouraged, though permitted, through the follow-up period:

- Topical therapies or emollients with anti-pruritic properties (including but not limited to anti-histamines, menthol or menthol derivatives, polidocanol, camphor, pramoxine, and capsaicin)
- Systemic therapies with recognized anti-pruritic properties (including but not limited to H1 antihistamines, doxepin, gabapentin, pregabalin, cannabinoids, kappa-opioid receptor agonists, and mu-opioid receptor antagonists)

Use of any excluded therapies (including those for the treatment of pruritus or PN lesions, or as rescue therapy) should be reported as soon as possible, and will be recorded as protocol deviations for subjects who receive them.

5.7.3 *Rescue Therapies*

The initiation of non-study drug therapy to treat worsening of pruritus or PN lesions, or flare of previously inactive skin disease, is strongly discouraged throughout the treatment period. However, should rescue therapy be required for the safety and well-being of the subject, such use will be recorded and analyzed (see [Section 8.2](#)). The subject may remain on study drug, unless the rescue therapy is an NK₁-R antagonist, a systemic biologic therapy, a strong CYP3A4 inhibitor, an investigational therapy, or any therapy that may jeopardize the subject's safety if study drug is continued, in the investigator's and/or Sponsor's opinion.

